10.2.1 Analysis of Adverse Events Prior to Protocol-Defined Treatment Switching

10.2.1.1 Adverse Events Overview

The number and percentage of subjects experiencing TEAEs will be summarized by treatment groups for the following AE categories.

- All TEAEs
- Treatment-emergent serious adverse events (SAEs)
- Treatment-emergent severe adverse events
- TEAEs reasonably possibly related to study drug
- TEAEs of special interest

- TEAEs leading to discontinuation of study drug
- TEAE leading to death

Additional AEs may be considered for tabulation/summary based on recommendations from Clinical and Safety as deemed appropriate.

For TEAEs of special interest, the point estimate and 95% CI (using normal approximation and separate group variance) will be provided for the treatment difference in AE percentage between Upadacitinib group and the placebo group.

10.2.1.2 Adverse Events by System Organ Class and Preferred Term

The number and percentage of subjects experiencing adverse events will be tabulated by SOC and MedDRA PT by treatment groups. The SOCs will be presented in alphabetical order, and the PTs will be presented in alphabetical order within each SOC.

The following summaries of adverse events will be generated:

- All TEAEs
- Treatment-emergent serious adverse events (SAEs)
- Treatment-emergent severe adverse events
- TEAEs reasonably possibly related to study drug
- TEAEs leading to discontinuation of study drug
- TEAE leading to death
- Frequent AEs (reported in 2% of subjects or more in any treatment group)

Subjects reporting more than one adverse event for a given MedDRA preferred term will be counted only once for that term (most severe incident for the severity tables and most related incident for the relationship tables). Subjects reporting more than one type of adverse event within a SOC will be counted only once for that SOC. Subjects reporting more than one type of adverse event will be counted only once in the overall total.

10.2.1.3 TEAEs by Maximum Severity

TEAEs will also be summarized by maximum severity by treatment groups. If a subject has an AE with an unknown severity, then the subject will be counted in the severity category of unknown, even if the subject has another occurrence of the same event with a severity present. The only exception is that if the subject has another occurrence of the same AE with the most extreme severity – severe. In this case, the subject will be counted under the severe category.

10.2.1.4 TEAEs by Relationship

TEAEs will also be summarized by relationship to Upadacitinib and Placebo, as assessed by the investigator, by treatment groups. If a subject has a TEAE with an unknown relationship, then the subject will be counted in the relationship category of "unknown," even if the subject has another occurrence of the same event with a relationship present. The only exception is if the subject has another occurrence of the same TEAE with a relationship assessment of "reasonable possibility." In this case, the subject will be counted under the "reasonable possibility" category.

10.2.1.5 Frequent ($\geq 2\%$) Adverse Events and Reasonably Possibly Related Adverse Events by System Organ Class and Preferred Term

TEAEs and reasonably possibly related AEs occurring for more than 2% of the subjects in any of the treatment groups will be summarized by MedDRA PT in decreasing frequency separately.

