6.1.3 Relationship to Study Drug

The Investigator will use the following definitions to assess the relationship of the AE to the use of study drug:

- | | |
|----------------------------------|---|
| Reasonable Possibility | After consideration of factors including timing of the event, biologic plausibility, clinical judgment, and potential alternative causes, there is sufficient evidence (information) to suggest a causal relationship. |
| No Reasonable Possibility | After consideration of factors including timing of the event, biologic plausibility, clinical judgment, and potential alternative causes, there is insufficient evidence (information) to suggest a causal relationship. |

For causality assessments, events assessed as having a reasonable possibility of being related to the study drug will be considered "associated." Events assessed as having no reasonable possibility of being related to study drug will be considered "not associated." In addition, when the Investigator has not reported a causality or deemed it not assessable, AbbVie will consider the event associated.

[figure not shown]
If an Investigator's opinion of no reasonable possibility of being related to study drug is given, an Other cause of event must be provided by the Investigator for the SAE.

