8.1.5 Safety Analysis

8.1.5.1 General Considerations

Safety analyses will be carried out using the Safety Analysis Set. Analyses will be conducted in primary analysis at Week 14, as well as for the entire study.

Safety analyses are based on treatments actually received. Safety will be assessed by treatment-emergent adverse events (TEAEs), physical examination, laboratory assessments, and vital signs. The number and percent of subjects experiencing TEAEs by treatment group will be tabulated by the Medical Dictionary for Drug Regulatory Activities (MedDRA[®]) system organ class (SOC) and preferred terms (PT). In addition,

summary of serious AEs and TEAEs by severity and relationship to study drug as assessed by the Investigators will be provided. SAEs, severe TEAEs, or TEAEs that lead to premature study discontinuation will be listed. The changes in vital signs, physical examination results, and clinical laboratory variables at each visit as compared to baseline will be summarized. Shift of laboratory values from baseline at defined time points will be tabulated.

Missing safety data will not be imputed.

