10.2.2.1 Overview of Adverse Events Rates per 100 Patient-Years of Study Drug Exposure

An overview of AEs per 100 patient-years of study exposure will be presented for Any Upadacitinib 15 mg QD for the following AE categories.

- All TEAEs
- Treatment-emergent serious adverse events (SAEs)
- Treatment-emergent severe adverse events
- TEAEs reasonably possibly related to study drug
- TEAEs of special interest

- TEAEs leading to discontinuation of study drug
- TEAE leading to death

The number of TEAEs reported, the total number of years of study drug exposure, and the TEAE rate per 100 patient-years will be presented for Any Upadacitinib 15 mg QD group.

Additional AEs may be considered for tabulation/summary based on recommendations from Clinical and Safety as deemed appropriate.

For TEAE of special interest, the point estimate and 95% CI (using normal approximation) will be provided for the Any Upadacitinib 15 mg QD group in AE rate per 100 patient-years (refer to [Appendix B](#)).

10.2.2.2 Adverse Events Rates per 100 Patient-Years of Study Drug Exposure by SOC and PT

For the Any Upadacitinib 15 mg QD treatment group, the TEAE rate per 100 patient-years of exposure as outlined in Section [10.2.2.1](#) will be calculated overall, for each SOC and each PT, for each of the following events:

- All TEAEs
- Treatment-emergent serious adverse events (SAEs)
- Treatment-emergent severe adverse events
- TEAEs reasonably possibly related to study drug
- TEAEs leading to discontinuation of study drug
- TEAE leading to death

10.2.2.3 Adverse Events of Special Interest Rates per 100 Patient-Years of Study Drug Exposure

The Adverse Events of Special Interest (AESI) categories will be summarized and presented for the Any Upadacitinib 15 mg QD treatment group using SOC and MedDRA PT (for adjudicated cardiovascular events, the CAC adjudicated categories will be used).

The AESI categories will be identified per Standard MedDRA Queries (SMQs)/Company MedDRA Queries (CMQs).

The Adverse Events of Special Interest (AESI) rate per 100 patient-years of exposure as outlined in Section 10.2.2.1 will be calculated overall, for each SOC and each PT, for each of the AESI listed in Section 10.2.1.6.

10.2.2.4 Listing of Serious Adverse Events (Including Deaths) and Adverse Events Leading to Study Drug Discontinuation

All serious adverse events (SAEs), deaths, and adverse events leading to discontinuation of study drug will be listed.

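### The protocol treats events with unreported or unassessable causality as associated with study drug; the SAP counts them as unknown in one Period 1 table and gives no rule for them in its other related-event tables

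*SAP*

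**What the plan says.** **Protocol 6.1.3** gives the investigator two categories, reasonable possibility and no reasonable possibility, and equates the first with being associated with study drug. For events that fit neither, it adds: "when the Investigator has not reported a causality or deemed it not assessable, AbbVie will consider the event associated".

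**Protocol 8.1.5.1** plans the output on the investigator's rating: "summary of serious AEs and TEAEs by severity and relationship to study drug as assessed by the Investigators will be provided". The same section says that missing safety data are not imputed, and SAP 10.1 repeats this.

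**SAP 10.2.1.4** specifies the Period 1 table: "TEAEs will also be summarized by relationship to Upadacitinib and Placebo, as assessed by the investigator, by treatment groups". Its rule for an unrated event is: "If a subject has a TEAE with an unknown relationship, then the subject will be counted in the relationship category of" unknown. The rating moves up to reasonable possibility only if the same subject has another occurrence of the same event rated that way.

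**Other related-event outputs in the SAP.** The category "TEAEs reasonably possibly related to study drug" appears in the Period 1 overview (10.2.1.1), the Period 1 tables by system organ class and preferred term (10.2.1.2), and the long-term rates (10.2.2.1 and 10.2.2.2). SAP 10.2.1.5 adds a frequency table covering "TEAEs and reasonably possibly related AEs occurring for more than 2% of the subjects in any of the treatment groups". None of these sections says where an event of unknown relationship goes. The SAP nowhere mentions the default in protocol 6.1.3.

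**The concern.** The two documents classify the same event differently. Under the protocol it belongs with the related events. In the one SAP table with a written rule it does not, and in the others its place is left to whoever programs the table.

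The by-relationship table at least shows an unknown row. The tables restricted to related events show no such row. An event left out of them is not visible there, and a reader who knows the protocol default would assume it had been counted. Those tables feed the benefit-risk summary. The protocol's default is the cautious one: relative to it, leaving events out can only leave the related count unchanged or lower it. The sponsor's own classification and its tables could then disagree about the same event.

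**Working it through.** The plan states no figure for related events or for events of unknown causality, so there is nothing to reproduce. The check is a comparison of rules followed by conditional arithmetic.

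**Step 1. Rules side by side**

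| Output | Protocol 6.1.3 default | SAP |
|---|---|---|
| Period 1 by relationship (10.2.1.4) | associated | unknown, with one exception |
| Period 1 overview (10.2.1.1) | associated | no rule |
| Period 1 by class and term (10.2.1.2) | associated | no rule |
| Frequent related events (10.2.1.5) | associated | no rule |
| Long-term rates (10.2.2.1, 10.2.2.2) | associated | no rule |

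**Step 2. Period 1 percentages.** Input: 85 planned subjects per arm (protocol 5.1). Let u be the number of subjects in an arm whose only candidate for a related event has unknown causality. The documents do not give u; 0 to 5 is assumed. Counting these subjects as related raises the arm's percentage by u/85:

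- u = 0: 0.0 points
- u = 1: 1.18 points
- u = 2: 2.35 points
- u = 3: 3.53 points
- u = 5: 5.88 points

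A subject who already has another event rated a reasonable possibility adds nothing to the overall percentage, so 1.18 points per affected subject is a maximum. The between-arm difference changes by (u in the upadacitinib arm minus u in the placebo arm)/85, which can have either sign.

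**Step 3. Frequent related events.** For a single preferred term, 1/85 = 1.18% and 2/85 = 2.35%. One reclassified subject can therefore carry a term over the 2% threshold and decide whether it is listed.

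**Step 4. Long-term rates.** Input: 104 weeks on drug for the arm starting on upadacitinib, and 104 − 14 = 90 weeks for the arm that switches. With full retention:

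- 85 × 104 + 85 × 90 = 16,490 weeks
- 16,490 × 7 / 365.25 = 316 patient-years
- 100/316 = 0.32 per 100 patient-years per event

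Allowing for dropout, 250 patient-years is assumed as a lower figure: 100/250 = 0.40 per 100 patient-years per event. The SAP's rate counts events, so a second related event in the same subject does not cancel this. The output has a single group, Any Upadacitinib 15 mg QD, so there is no between-arm comparison. Follow-up beyond Week 104 in five countries (SAP 4.1) enlarges the denominator at the final lock and makes the effect per event smaller.

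**The case against.** The strongest defence is that the two rules concern different assessors. Protocol 6.1.3 says how the sponsor will regard the event. Protocol 8.1.5.1 and SAP 10.2.1.4 both ask for a table of the investigator's assessment. If the investigator gave no rating, unknown is the accurate entry. The row is visible, and a reader can add it to the related row. The SAP also ranks cautiously: unknown overrides an occurrence of the same event rated unrelated. This stands as a reason to keep the unknown row in the investigator-assessed table. It does not settle the tables that show related events only, and protocol 6.1.3 is the only protocol text that classifies an event with no usable rating.

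The second defence is the rule against imputing missing safety data. It has some force for a rating never entered. It has little for an event judged not assessable, because that is a recorded answer. The SAP also already uses a cautious default for incomplete event data: SAP 10.2 presumes an event with an incomplete onset date to be treatment-emergent unless other evidence shows otherwise.

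Third, protocol 6.1 requires the investigator to record relationship for each adverse event, so unrated events should be exceptions. That is fair, and it limits the likely size.

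A reader might infer that related events and rates *are* understated, or that the SAP excludes unrated events from every related-event table. The documents support neither. They give no count of such events, and outside 10.2.1.4 the SAP is silent; no text directs exclusion.

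**Conclusion.** The inconsistency is real but conditional in effect. Protocol 6.1.3 and SAP 10.2.1.4 classify the same events differently, and the SAP does not carry the protocol default into any related-event output. If such events occur, related counts and rates may fall below those under the protocol rule.

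The size is at most 1.2 points per affected subject in a Period 1 arm and about 0.32 to 0.40 per 100 patient-years per event in the long-term rate. These figures rest on the planned 85 per arm and on an assumed 250 to 316 patient-years to Week 104. The total effect cannot be stated and is zero if every event was rated. No direction can be given for the Period 1 treatment difference.

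**What to change.** - **Week 104 and final safety analyses.** Add one rule to the SAP: an event whose causality is missing or not assessable counts as a reasonable possibility in every related-event output of 10.2.1 and 10.2.2. Footnote each table with the number of events so counted.
- **By-relationship table.** It may keep a visible unknown row, labelled as the investigator's assessment, with a note on how those events enter the related-event tables.
- **Week 14 data.** SAP 11.0 records that this lock was completed in February 2019. Leave the reported tables as they are and add one supplementary table with unknown counted as related.

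The cost is one SAP sentence, one derivation line, a footnote and one extra Period 1 table. The only downside is that related-event figures may look slightly less favourable. SAP 4.5 still has the Week 104 and final locks ahead, so the rule can be added before either analysis.

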10.2.1.6 Adverse Events of Special Interest

The Adverse Events of Special Interest (AESI) categories will be summarized and presented by treatment groups using SOC and MedDRA PT. The AESI categories will be identified by the following search criteria per Standard MedDRA Queries (SMQs)/Company MedDRA Queries (CMQs) in [Table 9](#) below. Adjudicated

cardiovascular events will be summarized and presented by treatment group using the CAC adjudicated categories.

Table 9. AESI for Upadacitinib with SMQs/CMQs/PTs Searches

AESI	Type of MedDRA Query	Broad or Narrow Search	SMQ/CMQ Search Criteria
Serious Infections	CMQ		"Infections" – Subset for SAEs
Opportunistic Infection excluding Tuberculosis and Herpes Zoster	CMQ		"Opportunistic Infection excluding Tuberculosis and Herpes Zoster"
Possible Malignancy	SMQ	Narrow	"Malignancies"
Malignancy	SMQ	Narrow	"Malignant tumours"
Non-Melanoma Skin Cancer (NMSC)	SMQ	Narrow	Skin Malignant tumours (narrow SMQ) removing Melanoma CMQ
Malignancy excluding NMSC			"Malignant tumours" Narrow SMQ removing NMSC output
Lymphoma	SMQ	Broad	"Malignant Lymphomas"
Hepatic Disorder	SMQ	Narrow	"Drug Related Hepatic Disorders"
Adjudicated Gastrointestinal Perforations	Based on adjudicated results (the identification of events to be adjudicated are described in the GI Perforation charter)		
Anemia	CMQ		"Non-Hemolytic and Non-Aplastic Anemias"
Neutropenia	CMQ		"Hematological Toxicity – Neutropenia"
Lymphopenia	CMQ		"Hematological Toxicity – Lymphopenia (Veliparib Product Specific)"

Table 9. AESI for Upadacitinib with SMQs/CMQs/PTs Searches (Continued)

AESI	Type of MedDRA Query	Broad or Narrow Search	SMQ/CMQ Search Criteria
Herpes Zoster	CMQ		"Herpes Zoster"
Creatine Phosphokinase (CPK) Elevation	PT		Search only for the PT of "Blood creatine phosphokinase increased"
Renal Dysfunction	SMQ	Narrow	"Acute Renal, Failure"
Active Tuberculosis	CMQ		"Active Tuberculosis"
Adjudicated Cardiovascular Events	Output from CAC		
MACE*			
Undetermined/Unknown Cause of Deaths			
Other Cardiovascular events			
Adjudicated Thrombotic Events	Output from CAC		
Venous Thromboembolic Events**			
Other Venous Thrombosis			
Arterial Thromboembolic Events (non-cardiac, non-neurologic)			

* MACE; Major Adverse Cardiovascular Events, defined as cardiovascular death, non-fatal myocardial infarction and non-fatal stroke.

** Venous thromboembolic events (VTE) include deep vein thrombosis (DVT) and pulmonary embolism (PE).

Additional AEs may be considered for tabulation/summary based on recommendations from Clinical and Safety as deemed appropriate.

10.2.2 Analysis of Long-Term Adverse Event

Long-term adverse events will be analyzed using event rates adjusted by cumulative exposure and will be based on the actual treatment received at the time of AE occurrence. According to the study design, randomized placebo subjects switch to Upadacitinib 15 mg

QD when entering Period 2, this analysis will be reported for Any Upadacitinib 15 mg QD subjects. The Any Upadacitinib 15 mg QD treatment group is defined as subjects who receive at least one dose of Upadacitinib 15 mg QD at any time during the study.

This includes AEs occurred under Upadacitinib 15 mg QD exposure from subjects starting on Upadacitinib 15 mg QD and subjects switching from placebo to Upadacitinib 15 mg QD.

Exposure-Adjusted Event Rate (EAER)

To adjust for potentially different follow-up time between treatment groups, EAER will be provided. For the purpose of event rate calculation, the numerator will be the total number of AEs reported for the event (i.e., a subject can contribute more than one event to the numerator) and the denominator will be the total exposure time among subjects under the treatment group. The number of AEs reported (numerator), the total number of years of study drug exposure (denominator), and the exposure-adjusted AE event rate per 100 patient-years calculated as $([\text{numerator (days)}/\text{denominator}])/365.25 \cdot 100$ will be presented for each treatment group. The EAER will be the main approach to evaluate AEs in the long-term analysis.

In addition, the exposure-adjusted incidence rate (censored at first event) will be conducted for AESI endpoints as deemed appropriate for long-term analysis.

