6.1.1 Definitions

6.1.1.1 Adverse Event

An AE is defined as any untoward medical occurrence in a patient or clinical investigation subject administered a pharmaceutical product and which does not necessarily have a causal relationship with this treatment. An AE can therefore be any unfavorable and unintended sign (including an abnormal laboratory finding), symptom, or disease temporally associated with the use of a medicinal (investigational) product, whether or not the event is considered causally related to the use of the product.

Such an event can result from use of the drug as stipulated in the protocol or labeling, as well as from accidental or intentional overdose, drug abuse, or drug withdrawal. Any worsening of a pre-existing condition or illness is considered an AE. Worsening in severity of a reported AE should be reported as a new AE. Laboratory abnormalities and changes in vital signs are considered to be AEs only if they result in discontinuation from

the study drug, necessitate therapeutic medical intervention, and/or if the Investigator considers them to be AEs.

An elective surgery/procedure scheduled to occur during a study will not be considered an AE if the surgery/procedure is being performed for a pre-existing condition and the surgery/procedure has been pre-planned prior to study entry. However, if the pre-existing condition deteriorates unexpectedly during the study (e.g., surgery performed earlier than planned), then the deterioration of the condition for which the elective surgery/procedure is being done will be considered an AE.

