Appendix B. EAER and Normal Approximation Based 95% Confidence Interval

Assume the occurrence of TEAE of special interest follows a Poisson distribution and let λ denote the rate of occurrence of TEAE under the total exposure time for a treatment group. Let n be the number of AEs reported in Any Upadacitinib 15 mg QD group. Let T be the total number of days exposed to study drug summed across all treated subjects in Any upadacitinib 15 mg QD group. Under the assumption that n follow Poisson distribution with parameters λT , the $\hat{\lambda} = n/T$.

Using normal approximation, the 95% confidence interval can be calculated by (Liu GF, et al. 2006.):

$$\hat{\lambda} \pm Z_{\alpha/2} \hat{\sigma}$$

Where $\hat{\sigma} = \sqrt{\frac{n}{T^2}}$

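### The long-term AESI rate counts every AE record but takes a plain Poisson standard error, so its 95% CI is too narrow wherever records repeat or cluster within subjects

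*SAP*

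**What the plan says.** - **Measure.** SAP 10.2.2: "The EAER will be the main approach to evaluate AEs in the long-term analysis". The numerator is all AEs reported for the event, the denominator is total exposure, and "a subject can contribute more than one event to the numerator".
- **What creates a record.** Protocol 6.1.1.1: "Worsening in severity of a reported AE should be reported as a new AE". SAP 10.2.2 has no rule for joining such records. By contrast, SAP 10.2.1.2 counts a subject once per preferred term in the Period 1 percentage tables.
- **Interval.** SAP 10.2.2.1: "For TEAE of special interest, the point estimate and 95% CI (using normal approximation) will be provided for the Any Upadacitinib 15 mg QD group". Appendix B supplies the method. It opens with "Assume the occurrence of TEAE of special interest follows a Poisson distribution", then "Let n be the number of AEs reported in Any Upadacitinib 15 mg QD group", takes T as total days of exposure, and sets the standard error to the square root of n/T². The interval is the estimate plus or minus the normal quantile times that standard error. There is no overdispersion or within-subject term.
- **Companion measure.** SAP 10.2.2 adds that "the exposure-adjusted incidence rate (censored at first event) will be conducted for AESI endpoints as deemed appropriate for long-term analysis". The version history (SAP 12.0) describes version 3.0 as bringing in the incidence rate for all AESI at future database locks. No CI method is given for this rate.

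**The concern.** The Poisson variance equals the mean only if records arise independently at a common rate. A worsening record exists only because an earlier record of the same episode exists, so the two are dependent by construction. Separate episodes in one subject also tend to cluster, because some subjects are more prone to an event than others. Both features make the variance of n larger than n, and Appendix B uses n.

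At stake is the stated precision of the main long-term safety measure, over up to two years of upadacitinib exposure at the Week 104 and final database locks. The categories plausibly affected are infections, hepatic disorder, CPK elevation and the cytopenias.

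**Working it through.** The documents give no AESI count, rate or interval to reproduce, so the Appendix B formula was applied as written and compared with what repeat records and clustering would imply.

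**Inputs from the documents.** 85 + 85 subjects; 104 weeks on upadacitinib for one arm and 90 for the other (SAP 4.2). With no dropout and no follow-up past Week 104, exposure is at most (85 × 104 + 85 × 90) × 7 / 365.25 = 316 patient-years (PY).

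**Assumed inputs (not in the documents).** q = probability that an episode carries one extra worsening record, 0 to 1. θ = variance of a gamma-distributed subject effect, 1 to 4.

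**Step 1: no repeat records.** Under a true Poisson count the Appendix B interval covers 92.6% at a mean of 10 events, 94.8% at 20, 94.9% at 50 and 95.0% at 300. It is not materially too narrow at moderate or large counts. At low counts it is poor for a different reason, the normal approximation: coverage is 63.2% at a mean of 1, 79.7% at 3 and 87.0% at 5. With zero events it gives [0, 0] per 100 PY, where exact limits at 316 PY give [0, 1.17].

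**Step 2: worsening records.** Let episodes be Poisson with mean m and let K = records per episode, 1 with probability 1 − q and 2 with probability q.

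- E[K] = 1 + q; E[K²] = (1 − q) + 4q = 1 + 3q.
- Mean of n = m(1 + q); variance of n = m(1 + 3q).
- Variance relative to Poisson: V = (1 + 3q)/(1 + q).
- Required half-width = √V × stated half-width; large-count coverage = 2Φ(1.96/√V) − 1.

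| q | V | CI should be wider by | Coverage of stated 95% CI |
|---|---|---|---|
| 0 | 1.00 | 0% | 95.0% |
| 0.10 | 1.30/1.10 = 1.18 | 9% | 92.9% |
| 0.25 | 1.75/1.25 = 1.40 | 18% | 90.2% |
| 0.50 | 2.50/1.50 = 1.67 | 29% | 87.1% |
| 1.00 | 4.00/2.00 = 2.00 | 41% | 83.4% |

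V does not contain m, so more events do not help. Coverage here is for the record rate, which is the quantity the EAER targets.

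*Illustration.* Take 20 episodes and q = 0.5, hence 30 records. The rate is 30/316 = 9.5 per 100 PY. The Appendix B half-width is 1.96 × √30 / 316 × 100 = 3.4, giving 6.1 to 12.9. Multiplied by 1.291 the half-width is 4.4, giving 5.1 to 13.9.

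**Step 3: would exact Poisson limits cure it?** No. The Appendix B interval is already 93.9%, 96.2% and 97.4% as wide as the exact one at 20, 50 and 100 events. Switching would widen it by 6.5%, 4.0% and 2.7% (1/0.939, 1/0.962, 1/0.974), against the 18% to 41% needed for q from 0.25 to 1.

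**Step 4: between-subject clustering alone.** With 170 subjects of equal exposure, V = 1 + θn/170. For θ = 2:

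- 5 events: V = 1.06, CI 3% wider, coverage 94.3%.
- 30 events: V = 1.35, 16% wider, 90.8%.
- 100 events: V = 2.18, 48% wider, 81.6%.

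Over θ from 1 to 4 the widening at 5 events is 1.5% to 6%; at 100 events it is 26% to 83%.

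**The case against.** **The EAER is openly an event rate.** A reader might infer that the AESI rates are inflated. The documents do not support that: SAP 10.2.2 says plainly that repeats count. The record rate exceeds the episode rate by the factor 1 + q, but it is a different quantity, and choosing between them is an estimand decision. What stands is the variance point, which applies to the record rate itself.

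**The effect is conditional.** A reader might also infer that the intervals are too narrow at every event count. They are not: without repeat or clustered records V is 1, a single record cannot be double counted, and Step 4 shows clustering alone is negligible for rare AESI. The documents give no frequency of repeat records. Protocol 6.1 limits them somewhat, since it asks for a diagnosis where known and allows intermittent events of similar nature and severity. Protocol 6.1.1.1 also makes laboratory abnormalities AEs only under stated conditions.

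**Not every AESI is exposed.** Table 9 of the SAP takes cardiovascular, thrombotic and gastrointestinal perforation events from adjudication, so whether worsening records add to those counts cannot be settled here. CPK elevation is one preferred term, so it can repeat only by worsening or recurrence. That paired liver-enzyme terms double the hepatic count is another tempting inference, but the SAP names the query without listing its terms.

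**Subject-level results are planned.** The first-event rate removes repeat counting, and the version history suggests it is meant for all AESI. SAP 10.3.3.2 and 10.3.3.3 summarise long-term laboratory and liver findings by subject. This reduces the harm considerably. It does not repair the interval, which SAP 10.2.2.1 attaches to the record rate, while the first-event rate is conditional in the body text and has no CI method.

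**No decision rests on it.** The analysis is descriptive, covers one group and feeds no test. That is correct and limits the weight of the point.

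**Conclusion.** The point holds for AESI categories with repeat or clustered records. Appendix B omits a source of variance that the protocol's own reporting rule creates, so the stated 95% CI is too short there, and neither larger counts nor exact Poisson limits correct it. If between 25% and 100% of episodes carry one extra worsening record, the interval should be about 18% to 41% wider, with large-count coverage between 90% and 83%. These percentages are assumptions, because the documents supply no record multiplicity. At q = 0 with no clustering the method is sound apart from its low-count behaviour. The primary efficacy conclusion is untouched. What is affected is the reported precision of the main long-term safety measure, and the correction is cheap enough to make before the remaining locks.

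**What to change.** 1. **Appendix B.** For AESI with enough events, replace sqrt(n)/T by the subject-level robust standard error, sqrt(Σ(nᵢ − λ̂Tᵢ)²)/T, where nᵢ and Tᵢ are subject i's record count and exposure and λ̂ = n/T; or bootstrap subjects. Prespecify what counts as enough: the Step 1 coverages suggest a switch point between 10 and 20. The robust form also collapses to zero width at zero events, so when events are few or zero report the first-event rate with an exact Poisson CI.
2. **SAP 10.2.2.** Align the conditional wording with the intent shown in the version history. Give the first-event incidence rate, with a stated CI method, for every AESI next to the EAER.
3. **Optional.** State that the EAER is a rate of AE records and may count several records per episode. Merging worsening records into episodes would be a change of estimand needing a linkage rule or medical review, and it is not required to correct the interval.

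Cost: SAP wording, slightly more programming, and wider intervals for some categories. No new data are needed.
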